## PROTOCOL AMENDMENT, VERSION 3.0

This protocol amendment serves to make the following changes.

Item No.	Change	Section
1	
Revised exclusion criteria 15 to exclude the use of systemic steroids (including dexamethasone), within 6 weeks prior to the Screening visit. The use of intratympanic steroids had already been excluded for 6 weeks prior to the Screening visit, therefore the revision adds systemic steroids to the exclusion. Systemic steroids may be used for treating sensorineural hearing loss and the 6-week exclusionary period prior to Screening will allow for any residual effects of the systemic steroid, if any, to stabilize prior to randomization.
 
The use of systemic steroids is also prohibited during the study and the prohibited therapies section has been revised accordingly.
	
Synopsis Section 4.3, Exclusion Criteria Section 7.1

## ABBREVIATIONS

AE	Adverse Event
ASHA	American Speech and Language Hearing Association
CRO	Clinical Research Organization
C-SSRS	Columbia-Suicide Severity Rating Scale
CYP2B6	Cytochrome P450 Isoform 2B6
dB	Decibel
eCRF	Electronic Case Report Form
EDC	Electronic Data Capture
GCP	Good Clinical Practice
Hz	Hertz
ICH	International Conference on Harmonisation
IRB	Institutional Review Board
MedDRA	Medical Dictionary for Regulatory Activities
mg	Milligram
mL	Milliliter
N	Number
NMDA	N-Methyl-D-Aspartic Acid
NRS	Numeric Rating Scale
OTO-311	Otonomy Investigational Product in poloxamer, Gacyclidine (Active Ingredient)
OTO-313	Otonomy Investigational Product in medium-chain triglyceride, Gacyclidine (Active Ingredient)
PK	Pharmacokinetics
PGIC	Patient Global Impression of Change
PT	Preferred Term
SAE	Serious Adverse Event
SAP	Statistical Analysis Plan
SD	Standard Deviation
SOC	System Organ Class
TEAE	Treatment Emergent Adverse Event
TFI	Tinnitus Functional Index
TSCHQ	Tinnitus Sample Case History Questionnaire

## SYNOPSIS

NAME OF SPONSOR/COMPANY:	Otonomy, Inc.
NAME OF FINISHED PRODUCT:	OTO-313
NAME OF ACTIVE INGREDIENT(S):	Gacyclidine
Protocol No.: 313-201901	
Title of Study: A randomized, double-blind, placebo-controlled Phase 1/2 study of OTO-313 given as a single intratympanic injection in subjects with subjective tinnitus	
Study Center(s): Part A of this study will be conducted at 1 site in the United States and Part B will be conducted at approximately 20 sites in the United States	
Study Period: approximately 12 months	Phase of Development: 1/2
Study Design: 
This is the first study of intratympanic OTO-313 in subjects with tinnitus and is composed of 2 parts. Part A is a randomized, double-blind, placebo-controlled Phase 1 cohort to evaluate the safety and plasma pharmacokinetics (PK) of one dose level (0.11 mg) of OTO-313 in subjects with unilateral or bilateral subjective tinnitus. Eight eligible subjects will be randomly assigned to either OTO-313 (6 subjects) or placebo (2 subjects) for intratympanic injection to a single (study) ear. Subjects in Part A will undergo blood sampling for plasma concentration testing of gacyclidine including (+) and (-) enantiomers of gacyclidine (and possibly its metabolites) on Days 1, 2, and 8 and will be observed for safety and exploratory efficacy for 28 days.
 
If acceptable safety and tolerability is observed in Part A (as determined by review of data through Day 8 for all subjects by the Safety Review Committee), Part B of the study will be initiated. Part B is a randomized, double-blind, placebo-controlled cohort of subjects with unilateral subjective tinnitus to evaluate the safety and preliminary efficacy of OTO-313. Fifty subjects will be randomly assigned, using a 1:1 allocation ratio, to intratympanic injection of either 0.32 mg OTO-313 or placebo to the affected (study) ear. If acceptable safety and tolerability is observed for the first 12 subjects dosed in Part B (as determined by review of data through Day 8 by the Safety Review Committee), the remaining subjects in Part B will be enrolled. In the event that adverse safety findings occur with 0.32 mg OTO-313 in the first 12 subjects, Part B subjects may be enrolled using the 0.11 mg dose level of OTO-313, and enrollment expanded so that 50 subjects are randomized to that dose level or to placebo. All subjects in Part B will be observed for safety and preliminary efficacy for 8 weeks following dosing. Blood samples for PK analysis will be obtained on Day 1 and on Day 8 in a subset of approximately 16 subjects at selected sites in Part B.
	
Study Objectives:	
Part A	
Primary:	

To evaluate the safety and tolerability of OTO-313 in subjects with unilateral or bilateral tinnitus.

	
Secondary:	

To assess the plasma PK of gacyclidine including (+) and (-) enantiomers of gacyclidine (and possibly its metabolites).

	
Part B	
Primary:	


To evaluate the safety and tolerability of OTO-313 in subjects with unilateral tinnitus.

	
Secondary:	

To examine the preliminary efficacy of OTO-313 in subjects with unilateral tinnitus, as measured by the change from Baseline in the Tinnitus Functional Index (TFI).

	

NAME OF SPONSOR/COMPANY:	Otonomy, Inc.
NAME OF FINISHED PRODUCT:	OTO-313
NAME OF ACTIVE INGREDIENT(S):	Gacyclidine

 
To assess, in a subset of subjects, the plasma PK of gacyclidine including (+) and (-) enantiomers of gacyclidine (and possibly its metabolites).
 
 
Exploratory:
 
 
To explore the preliminary efficacy of OTO-313 on tinnitus annoyance using a subject-reported Numeric Rating Scale (NRS).
 
To explore the preliminary efficacy of OTO-313 on tinnitus loudness using a subject-reported NRS.
 
To explore the preliminary efficacy of OTO-313 on tinnitus severity using the Patient Global Impression of Change (PGIC).
 
	

Methods:
 
Part A
 
Part A will be conducted at 1 site in the United States and will involve 1 overnight stay in the research unit. The duration of Part A for each subject will be approximately 4-6 weeks, including an up to 2-week Screening period and a 4-week follow-up period.
 
After informed consent and Screening, eligible subjects will be randomized to OTO-313 or placebo at the Baseline visit (Day 1). Eight subjects will receive either 0.11 mg OTO-313 (N=6) or placebo (N=2). Plasma samples for pharmacokinetic (PK) analysis will be obtained on Day 1 (pre-dose, 0.5, 1, 2, 4, 8, and 12 hours post-administration), Day 2 (24 hours post-administration), and Day 8. Subjects will remain overnight in the research unit on Day 1 and will be discharged on Day 2. Additional follow-up visits for safety and efficacy assessments will be conducted on Day 8, Day 15, and Day 29 (end of study) or upon early termination from the study.
 
If acceptable safety and tolerability is observed for 8 days post-administration in Part A in all subjects, Part B will be initiated with the 0.32 mg dose level of OTO-313 (see Safety Data Review).
 
Part B
 
Part B will be conducted at approximately 20 sites in the United States. The duration of Part B for each subject will be approximately 10-12 weeks, including an up to 2-week Screening period, a 2-week Lead-in assessment period, and an 8-week Follow-Up period. If acceptable safety and tolerability is observed for 8 days for the first 12 subjects dosed (see Safety Data Review), the remaining subjects in Part B will be enrolled. In the event that adverse safety findings occur with 0.32 mg OTO-313 in the first 12 subjects, Part B subjects may be enrolled using 0.11 mg OTO-313, and enrollment expanded so that 50 subjects are randomized to this (lower) dose level or to placebo in order to reach the target number of subjects for Part B.
 
After informed consent and Screening, potential subjects will begin a 2-week lead-in assessment period. During this time, subjects will enter daily tinnitus annoyance and tinnitus loudness severity into an electronic diary using the appropriate Numeric Rating Scales (NRS) for each symptom. Subjects must have completed the tinnitus electronic diary on 4 of the last 7 days of the Lead-in period for eligibility. Subjects will also complete the Tinnitus Functional Index (TFI) at both the Screening visit and the Baseline visit (Day 1). Subjects must have a score of <math>\geq 25</math> at each TFI assessment for eligibility. At the Baseline visit (Day 1), eligible subjects will be randomized to OTO-313 or placebo using a 1:1 allocation ratio.
 
After a single intratympanic injection with OTO-313 or placebo to the affected (study) ear on Day 1, subjects will continue to record their tinnitus annoyance and tinnitus loudness on a daily basis using the electronic diary during the 8-week follow-up period. Subjects will complete the TFI at study visits on Day 1 (Baseline), Day 15, Day 29, and Day 57 (end of study). Additional safety and/or exploratory assessments will also be completed at Day 1 (Baseline), Day 8, Day 15, Day 29, and Day 57 (end of study) or upon early termination from the study.
	

NAME OF SPONSOR/COMPANY:	Otonomy, Inc.
NAME OF FINISHED PRODUCT:	OTO-313
NAME OF ACTIVE INGREDIENT(S):	Gacyclidine

In a subset of 16 subjects at selected sites, blood samples for PK analysis will be obtained on Day 1 (pre-dose and 1-hour post-administration) and on Day 8.
 
Safety Data Review
 
The decision to proceed with initiation of dosing in Part B, and subsequent dosing decisions, will be made by a Safety Review Committee. The Safety Review Committee will include at a minimum the Medical Monitor, the Investigator at the Phase 1 research unit, and the Clinical Representative of the Sponsor. Safety data, including adverse events, clinical safety laboratory measurements, audiometry, otoscopy, tympanometry, and C-SSRS data through Day 8, will be evaluated and the decision to proceed will be based on the clinical significance of any adverse events or suspected investigational product-related findings. Initially, all data will be reviewed in a blinded manner with regard to treatment assignment. The treatment assignment for an individual subject may be unblinded, if deemed necessary to enable medical care or study decision-making by the Safety Review Committee.
	

Number of Subjects:
 
The planned sample size for this study is 58 to 70 subjects (8 subjects in Part A and 50 to 62 subjects in Part B).
	

Diagnosis and Main Criteria for Inclusion:
 
To be eligible for this study, each of the following criteria must be satisfied with a “YES” answer (unless not applicable):
 
Part A only
 
 
1. Subject has subjective unilateral or bilateral tinnitus and is consistently aware of their tinnitus throughout much of the waking day.
 
 
Part B only
 
 
2. Subject has subjective unilateral tinnitus and is consistently aware of their tinnitus throughout much of the waking day.
 
3. Subject’s self-reported duration of tinnitus is between 1 month and 6 months (30 to 180 days) prior to signing informed consent.
 
4. Subject has an overall score of <math>\geq 25</math> on the TFI at Screening and Baseline (Day 1) visits.
 
5. Subject is able to use the electronic diary to complete their daily tinnitus ratings and has completed at least 4 of the last 7 days of diary entries during the 2-week Lead-in period.
 
 
Part A and B
 
 
6. Subject is a male or female aged 18 to 75 years, inclusive.
 
7. Subject’s tinnitus is likely of cochlear origin, e.g., associated with sensorineural hearing loss; acute hearing loss from noise trauma, barotrauma, or traumatic cochlear injury (acute acoustic trauma, blast trauma, middle ear surgery, inner ear barotrauma); age-related hearing loss; resolved otitis media; ototoxic drug exposure.
 
8. Female subjects of childbearing potential [i.e., not surgically sterile and/or not post-menopausal (<math>\geq 12</math> months since last menstrual period and 45 years of age or older)] must have a negative urine pregnancy test at Baseline (Day 1). Women of childbearing potential who are not abstinent from sex with male partners must use effective methods of contraception for the duration of the study including: established use of oral, injected, or implanted hormonal methods of contraception; placement of an intrauterine device or intrauterine system; or “double barrier” methods including a combination of male condom with either diaphragm or cervical cap with spermicide. Female subjects of childbearing potential must also refrain from egg donation or retrieval for the duration of the study.
 
	

NAME OF SPONSOR/COMPANY: Otonomy, Inc.

NAME OF FINISHED PRODUCT: OTO-313

NAME OF ACTIVE INGREDIENT(S): Gacyclidine

9. Male subjects (unless surgically sterile) who are not abstinent from sex with female partners of childbearing potential must agree to use an effective contraceptive method (as detailed for Inclusion Criteria 8) for the duration of the study. Male subjects must refrain from sperm donation for the duration of the study.
10. Subject is willing to comply with the protocol and attend all study visits.
11. Subject is able to provide written informed consent after the scope and nature of the investigation have been explained, and before the initiation of any study-related procedures.

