### 3.2. Part B

Part B will be conducted at approximately 20 sites in the United States. The duration of Part B for each subject will be approximately 10-12 weeks, including an up to 2-week Screening period, a 2-week Lead-In assessment period, and an 8-week Follow-Up period. If acceptable safety and tolerability is observed for 8 days for the first 12 subjects dosed (see Safety Data Review in [Section 14.6.1](#)), the remaining subjects in Part B will be enrolled. In the event that adverse safety findings occur with 0.32 mg OTO-313 in the first 12 subjects, Part B subjects may be enrolled using 0.11 mg OTO-313, and enrollment expanded so that 50 subjects are randomized to this (lower) dose level or placebo to reach the target number of subjects for Part B.

[figure not shown]
After informed consent and Screening, potential subjects will begin a 2-week Lead-in assessment period. During this time, subjects will enter daily tinnitus annoyance and tinnitus loudness into an electronic diary using a Numeric Rating Scale (NRS). Subjects must have completed the tinnitus electronic diary on 4 of the last 7 days of the Lead-in period for eligibility. Subjects will also complete the Tinnitus Functional Index (TFI) at both the Screening visit and the Baseline visit (Day 1). Subjects must have a score of  $\geq 25$  at each TFI assessment for eligibility. At the Baseline visit (Day 1), eligible subjects will be randomized to OTO-313 or placebo using a 1:1 allocation ratio.

After a single intratympanic injection with OTO-313 or placebo to the affected (study) ear on Day 1, subjects will continue to record their tinnitus annoyance and tinnitus loudness on a daily basis using the electronic diary during the 8-week follow-up period. Subjects will complete the TFI at study visits on Day 1 (Baseline), Day 15, Day 29, and Day 57 (end of study). Additional safety and/or exploratory assessments will also be completed at Day 1 (Baseline), Day 8, Day 15, Day 29, and Day 57 (end of study) or upon early termination from the study. In a subset of approximately 16 subjects in Part B, blood samples for PK analysis will be obtained on Day 1 (pre-dose and 1-hour post-administration) and on Day 8.

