**Figure 1. Study Design Schematic – Part A**

**Figure 2. Study Design Schematic – Part B**

## **4. STUDY POPULATION**

### **4.1. General Considerations**

Approximately 58 to 70 subjects (8 subjects in Part A and 50 to 62 subjects in Part B) will be enrolled at approximately 20 study sites in the United States. Subjects will be eligible if they meet all of the following inclusion criteria and none of the exclusion criteria.

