## **5. RANDOMIZATION AND BLINDING**

### **5.1. Overview**

In Part A, 8 enrolled subjects will be assigned randomly to 0.11 mg OTO-313 or placebo using a 6:2 allocation ratio, based on a computer-generated randomization schedule.

- 0.11 mg OTO-313; single (0.2 mL volume) intratympanic injection to the affected (study) ear
- Placebo (vehicle); single (0.2 mL volume) intratympanic injection to the affected (study) ear

In Part B, 50 enrolled subjects will be assigned randomly to 0.32 mg OTO-313 (or 0.11 mg OTO-313 after Safety Data Review; see [Section 14.6.1](#)) or placebo using a 1:1 allocation ratio, based on a computer-generated randomization schedule.

- 0.32 mg OTO-313; single (0.2 mL volume) intratympanic injection to a single, affected (study) ear
- Placebo (vehicle); single (0.2 mL volume) intratympanic injection to a single, affected (study) ear

In the event that adverse safety findings occur with 0.32 mg OTO-313 in the first 12 subjects, Part B subjects may be enrolled using 0.11 mg OTO-313, and enrollment expanded so that 50 subjects are randomized to this (lower) dose level or placebo to reach the target number of subjects for Part B.

A subset of approximately 16 subjects will undergo PK testing at select study sites in Part B.

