### **5.2. Enrollment Procedures**

#### **5.2.1. Assignment of Subject Identification Numbers**

At the Screening visit (Visit 1), subjects signing the informed consent will be assigned a sequential subject identification number by the site. Once assigned, the subject identification number will not be re-assigned and should not be changed. This number will be used to identify the subject throughout the study, including the Screening and Lead-in periods. Subjects will be considered enrolled into the study once they are randomized.

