### **5.2.3. Randomization Algorithm**

In Part A, subjects will be randomized in a 6:2 ratio (OTO-313:placebo) of treatment groups using a permuted block randomization algorithm. In Part B, subjects will be randomized in a 1:1 ratio (OTO-313:placebo) of treatment groups using a permuted block randomization algorithm.

The randomization process will be deployed via WebEZ which is accessible 24 hours a day to authorized users. The subject's randomization number will determine the randomized treatment assignment. Investigational product kits will be labeled with a unique kit number using a separate and independent randomization algorithm. Numbered kits will be dispensed based on the treatment assignment.

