#### **10.2.2. Replacements**

In order to meet the target for 50 evaluable subjects for Part B, subjects who discontinue participation in the study for non-safety related reasons will be replaced up to a maximum of 10 additional subjects.

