### **11.2. Analysis Sets**

The intent-to-treat analysis set includes all subjects from Part A and all subjects that are randomized in Part B. All efficacy analyses will be carried out in the intent-to-treat analysis set. Subjects will be included in the group to which they were randomized.

The safety analysis set includes all subjects who receive study treatment. The safety analysis set will be used for all summaries of safety. In safety analyses and summaries, subjects will be included in the treatment group based on the treatment that was received.

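### Does the planned enrolment of 58 to 70 wrongly leave out the permitted replacements, and is the Day 57 comparison undefined, if the Part B dose is switched?

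*Combined protocol and SAP*

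**What the plan says.** The Synopsis (Number of Subjects) says: "The planned sample size for this study is 58 to 70 subjects (8 subjects in Part A and 50 to 62 subjects in Part B". Section 4.1 repeats the range, prefaced by a word of approximation: "Approximately 58 to 70 subjects (8 subjects in Part A and 50 to 62 subjects in Part B) will be enrolled".

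Section 3.2 provides for adverse safety findings in the first 12 Part B subjects. The lower dose may then be used, with "enrollment expanded so that 50 subjects are randomized to this (lower) dose level or placebo". Section 5.1 repeats this.

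Section 10.2.2 aims at 50 evaluable Part B subjects and says that "subjects who discontinue participation in the study for non-safety related reasons will be replaced up to a maximum of 10 additional subjects". It makes no exception for a dose switch. Under Section 5.2.1, "Subjects will be considered enrolled into the study once they are randomized", so a replacement counts as an enrolled subject.

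On the analysis, Section 11.2 puts every randomised Part B subject in the intent-to-treat set and adds: "Subjects will be included in the group to which they were randomized". Section 5.1 names the active arm by dose: "50 enrolled subjects will be assigned randomly to 0.32 mg OTO-313 (or 0.11 mg OTO-313 after Safety Data Review". Section 5.2.3 names it only by product: "In Part B, subjects will be randomized in a 1:1 ratio (OTO-313:placebo) of treatment groups". Section 11.4.8 fits an ANCOVA with treatment group as the factor and does not list the levels of that factor.

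**The concern.** The protocol foresees two separate reasons for enrolling more than 50 subjects in Part B: a dose switch and replacement of discontinued subjects. The stated range covers the first but not the two together. A reader who takes 62 and 70 as ceilings would find that Section 10.2.2 permits 10 more.

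The second worry concerns the Day 57 TFI comparison. After a switch, Part B would hold subjects on two doses and placebo subjects from two periods. If the active arm is read as the product, as in Section 5.2.3, the doses might be pooled and the contrast would no longer estimate the effect of one dose. If it is read by dose, as in Section 5.1, they stay apart. Nothing says whether placebo subjects from the first 12 join the later placebo subjects. At stake would be a main efficacy contrast whose make-up could be settled after the data are known.

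**Working it through.** **1. The stated range.** Inputs: Part A 8 and Part B 50 (Section 11.1); first cohort 12 and a fresh 50 after a switch (Section 3.2).

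- No switch: Part B 50; study 8 + 50 = 58.
- Switch: Part B 12 + 50 = 62; study 8 + 62 = 70.

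Both ends are reproduced exactly with no replacements.

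**2. Adding the replacements.** Input: at most 10 (Section 10.2.2).

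- No switch: Part B 50 + 10 = 60; study 68. Both fall inside the range.
- Switch: Part B 62 + 10 = 72; study 80. The excess is 10/62 = 16% and 10/70 = 14%.

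The figures 72 and 80 need three things together: a switch after all 12 are dosed, all 10 replacements used, and a target of 50 evaluable subjects that must be met wholly from the post-switch cohort. If the first 12 could count toward the target, 62 − 10 = 52 would remain after 10 discontinuations and no replacement would be needed.

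**3. The stated power.** Inputs (Section 11.1): difference 12, SD 17, one-sided alpha 0.05, 25 per arm.

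- Noncentrality = 12 / (17 × √(1/25 + 1/25)) = 2.496.
- One-sided critical t on 48 degrees of freedom = 1.677.
- Power = 0.793 from the noncentral t distribution, or 0.803 by the normal approximation. Both agree with the stated 80%.

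Replacements serve to keep 50 evaluable subjects, so this figure does not depend on whether the range includes them.

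**4. Possible contrasts after a switch.** Two assumptions are needed that the documents do not supply: a 6/6 split of the first 12, and an effect of *e* points for the first dose when the later dose has 12.

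- Later dose v later placebo (25 v 25): power 0.793.
- Later dose v all placebo (25 v 31): power 0.828.
- Pooled doses v all placebo (31 v 31): mean difference (25 × 12 + 6*e*)/31, with SD kept at 17.

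| *e* | Mean difference | Power |
|---|---|---|
| 0 | 9.68 | 0.716 |
| 6 | 10.84 | 0.799 |
| 12 | 12.00 | 0.865 |
| 18 | 13.16 | 0.914 |

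The two contrasts that keep the doses apart have at least the planned power. Pooling can raise or lower it, depending on an effect nobody knows.

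**5. What the text favours.** Sections 3.2 and 5.1 describe subjects as randomised to a dose level or placebo, and rebuild a full 50 at the later dose. That step would serve little purpose if the doses were to be pooled. Section 11.2 then analyses subjects as randomised. Section 5.2.3 describes the allocation ratio and gives no instruction to pool.

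**The case for a change.** The case for a change is that the upper figure exists only to cover the switch, so it ought to be right on that path. Section 4.1 speaks of subjects who will be enrolled, replacements are enrolled once randomised, and no passage says the range excludes them. The switch text ties the fresh 50 to the Part B target, which favours counting replacements on top of 62. A shortfall of 10 is more than rounding.

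As arithmetic, this stands. It does not show a contradiction. The range is given as planned in the Synopsis and as approximate in Section 4.1, its lower end also omits replacements, and Section 10.2.2 calls them additional. Nor is there a traced consequence. Section 12.4 drives supply from inventory thresholds set for each site, not from the enrolment range, and the IRB approves a protocol that already contains Section 10.2.2.

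The grouping argument is stronger. The handling of first-cohort placebo subjects is unstated, and Section 14.6.1 lets the Safety Review Committee unblind individuals. Sections 11.5.1 and 11.6 defer some details to a SAP but do not name this one, and no separate SAP text was available to check. Against that, Section 5.3 withholds the randomisation schedule until the database is final, so the comparison can be fixed while the data are still blinded.

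**Conclusion.** No change follows. On the switch path, permitted enrolment could exceed the stated upper figures by 10 (72 against 62 in Part B, 80 against 70 overall). That compares a maximum including replacements with a plan that omits them throughout. Correcting it would alter no analysis, power figure or conclusion. Without a switch, 60 and 68 lie inside the range.

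The grouping question is missing detail of a kind that analysts fill sensibly. The dose-level wording and the as-randomised rule point to comparing the later dose with placebo and reporting first-dose subjects separately. On the assumed 6/6 split and a 12-point effect, power is then 0.79 or 0.83, depending on whether first-cohort placebo subjects are included. The wider span of 0.72 to 0.91 arises only under pooling, which no passage requires, and it rests on assumed first-dose effects of 0 to 18 points. Efficacy is in any case a secondary, preliminary objective of Part B (Section 2.2.2). A clause saying that the range excludes replacements, and a sentence defining the groups after a switch, would be courtesies to the reader.
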